9.3 Missing Data

No missing data will be imputed.

9.4 Statistical Methodology

9.4.1 Data Summary

Descriptive statistics will be computed for all baseline conditions and demographic parameters. That is, for continuous data, the N, mean, median, standard deviation, minimum and maximum will be computed. For categorical data, the frequency will be computed. The data will be presented by appropriate subgroups (e.g., center, gender).

A Kaplan-Meier survivorship curve will be displayed for revision and/or removal of the Secur-Fit Advanced Hip Stem for aseptic loosening or device-related femoral fracture.

A Kaplan-Meier survivorship curve will be displayed for all-cause revision and/or removal of the Secur-Fit Advanced Hip Stem.

For the additional data collected according to Section 2.1.3, data will be summarized according to visit. For parameters represented by continuous variables (e.g., ROM), the

summaries will consist of the N, mean, median, standard deviation, minimum, and maximum values. For categorical variables (e.g., Mobility from EQ-5D), the frequency and percentage in each category will be presented. A paired t-test will be performed to evaluate the change in clinical and patient outcomes, preoperative to 5 years within the Secur-Fit Advanced Hip Stem. The 1-year, 2-year and 5-year SF-12, LEAS and HHS will be presented with respect to improvement from preoperative scores.

For the Follow-up Questionnaire, frequency and percentage will be computed for each category according to visits. Applicable lists based on Follow-up Questionnaire will be generated to capture AEs.

For radiographic data, data will be presented according to visits for available parameters. Frequency and percentage will be computed for radiolucency according to visit. Lists will be generated for migration over time. Radiographic failure will be evaluated, where radiographic failure is defined as subsidence of greater than 5 mm, migration of greater than 5° in any direction or at least 2 mm radiolucency in all zones within a single view.

Documentation of statistical analyses utilizing SAS® software version 9.1.3 or higher.

9.4.2 Sample Size Justification

With a reference value of 99% of success rate at 5 years, under the regular assumptions of 5% significance level (or 95% one-sided confidence interval), 80% power, 2.5% non-inferiority margin, the sample size is 277. After factoring a 15% lost to follow-up rate, the final sample size is 326. A significant decrease in screening/enrollment occurred after 2018, resulting in a final sample size of 314 cases.

9.4.3 Interim Analyses

No interim analysis is planned.

9.4.4 Analysis Population

Per Protocol Population: The study population for analysis will include all non-censored subjects who receive the Secur-Fit Advanced Hip Stem and are available for efficacy evaluation.

The primary and secondary efficacy analyses will be based on the per protocol population.

Safety Population: The safety population will include all non-censored subjects who received the Secur-Fit Advanced Hip Stem.

The safety analysis will be based on the safety population.

10 Study Procedures

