- K. Patient has an active or suspected latent infection in or about the affected hip joint at time of study device implantation.
- L. Patient has a neuromuscular or neurosensory deficiency that would create an unacceptable risk of instability, prosthesis fixation failure or complications in postoperative care, or which limits the ability to evaluate the safety and efficacy of the device.

Inclusion/Exclusion Criteria

Exclusions (continued): M. Patient has bone stock that is inadequate for support or fixation of the prosthesis, or is diagnosed with a systemic disease (e.g. Lupus Erythematosus) or a metabolic disorder (e.g. Paget's Inclusion/Exclusion disease) leading to progressive bone deterioration. Criteria N. Patient is immunologically suppressed or receiving steroids in excess of normal physiological requirements (e.g. > 30 days). O. Patient has a known sensitivity to device materials. P. Patient is a prisoner. **Secur-Fit Advanced Hip Stem** Required Components: Secur-Fit Advanced Femoral Stem The femoral component must be used in a cementless application. Stryker acetabular components and femoral bearing heads must be **Study Device** used according to this study protocol. The following ancillary devices are permissible: Compatible Stryker femoral bearing heads Compatible Stryker acetabular shells, liners and inserts The compatible Stryker head and acetabular components are listed in the surgical protocol.

Primary Objective:

5-year success rate of the Secur-Fit Advanced Hip Stem with an endpoint of revision for aseptic loosening or device-related femoral fracture will be compared with a 99% success rate, with a 2.5% noninferiority margin.

Statistical Methodology

Secondary Objectives:

- The Kaplan-Meier survival curve of revision/removal for the Secur-Fit Advanced Hip Stem will be displayed.
- The rate of device-related femoral fracture within 30 days of index THA will be reported.
- The mean amount of unintended exposure or countersink of the femoral component upon final seating will be presented.

Evaluation Schedule

Evaluation	Preop X-rays (-1 yr) CRFs (-4 mos)	Intraop	6 weeks (+ 3 wks)	1 year (+ 2 mos)	2 years (+ 2 mos)	3 years (+ 3 mos)	4 years (+ 4 mos)	5 years (+ 4 mos)	6 years (+ 4 mos)	7 years (+ 4 mos)	8 years (+ 4 mos)	9 years (+ 4 mos)	10 years (+ 4 mos)
Inclusion/ Exclusion	x												
Demographics & Medical History	х												

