9.1.3 Primary Efficacy Analysis

The primary hypothesis to be tested will be that the success rate at 5 years postoperative with the Secur-Fit Advanced Hip Stem is not worse than 99% with a non-inferiority margin of 2.5%.

That is, the following hypothesis will be tested:

Ho: Pt <= 99% - 2.5% HA: Pt > 99% - 2.5%

Here, Pt is the success rate at 5 years postoperative with the Secur-Fit Advanced Hip Stem

A 90% two-sided confidence interval will be computed for the success rate at 5 years. If the lower bound of the confidence interval is greater than 96.5%, then the non-inferiority hypothesis will be supported.

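### Section 9.4.4 restricts the efficacy and safety populations to undefined non-censored subjects, and 9.1.3 names neither estimator nor interval method for the 96.5% test

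*Combined protocol and SAP*

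**What the plan says.** Protocol 9.4.4 defines the per protocol population as "all non-censored subjects who receive the Secur-Fit Advanced Hip Stem and are available for efficacy evaluation". It adds: "The primary and secondary efficacy analyses will be based on the per protocol population". For safety: "The safety population will include all non-censored subjects who received the Secur-Fit Advanced Hip Stem". No section says who counts as censored or what makes a case available for evaluation.

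Protocol 9.1.3 states: "A 90% two-sided confidence interval will be computed for the success rate at 5 years". The decision rule follows: "If the lower bound of the confidence interval is greater than 96.5%, then the non-inferiority hypothesis will be supported". Level, sidedness and threshold are therefore fixed. The section does not say whether the rate is a binomial proportion or a Kaplan-Meier estimate, or how the interval is calculated.

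Section 9.3 says "No missing data will be imputed". Section 9.4.1 provides that a Kaplan-Meier "survivorship curve will be displayed for revision and/or removal of the Secur-Fit Advanced Hip Stem for aseptic loosening" or device-related femoral fracture, which is the primary endpoint. The Synopsis has a similar line for revision or removal: "The Kaplan-Meier survival curve of revision/removal for the Secur-Fit Advanced Hip Stem will be displayed". Neither links the curve to the 96.5% test. Sections 2.1.3 and 7.4 say that the questionnaires are collected so that this curve can be drawn.

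Section 10.3 ends a subject's participation at death, loss, withdrawal or any stem revision. Only stem revision or removal for aseptic loosening or device-related fracture is a failure. The section does not say how deaths and other-cause stem revisions enter the primary denominator.

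**The concern.** There are two gaps.

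**Who is analysed.** A censored case is ordinarily one whose follow-up stops before the endpoint without an event. Excluding such cases makes membership of the analysis set depend on what happens after surgery. Seating height is measured during surgery, fracture is assessed to 30 days, and perioperative serious events end at discharge. A case lost in year 3 has complete data on all of these, yet would leave the tables. For the 5-year rate, a failure seen before a potential loss stays in, while an event-free case lost before 5 years goes out, along with its event-free follow-up.

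**How the rate is tested.** Very few failures are expected, and at such counts interval methods differ by more than half a percentage point. In an open-label single-arm study, a rule left open can be settled after the failure count is known. The non-inferiority verdict could then rest on that choice.

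**Working it through.** **Inputs.** Reference 99%, margin 2.5 points, so threshold 96.5% (9.1.3). One-sided 5%, power 80%, 277 evaluable, 15% loss, 326, then 314 cases (9.4.2).

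**1. The plan's own sample size.** One-sample proportion test, normal approximation:

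n0 = [(1.645·√(0.965·0.035) + 0.842·√(0.99·0.01)) / 0.025]² = 238.4

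With continuity correction: n0/4·(1 + √(1 + 2/(n0·0.025)))² = 276.99, so 277. Then 277/0.85 = 325.9, so 326. Both figures reproduce. This supports reading the primary analysis as a proportion in evaluable cases, although the plan does not say so.

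**2. Cases affected.** 314 × 0.15 = 47.1, about 47 lost; 314 × 0.85 = 266.9, about 267 evaluable.

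**3. Bias of the proportion.** Assume 15% loss, uniform over 5 years and unrelated to failure. Let q be the true failure rate. If failures are also even over 5 years, half of those in cases due to be lost come before the loss, so the observed failure share is q·(1 − 0.15·0.5) = 0.925q. The event-free evaluable share is 0.85·(1 − q).
- q = 1%: 0.00925/(0.00925 + 0.8415) = 1.09%, so success reads 98.91%, about 0.1 point low.
- q = 3.5%: 0.03238/(0.03238 + 0.82025) = 3.80%, so success reads 96.20%, 0.3 points low.

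With half the failures within 90 days, the shortfall is about 0.1 and 0.4 points.

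**4. Lower bounds of the two-sided 90% interval, n = 267.**

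| Failures | Wald | Wilson | Exact |
|---|---|---|---|
| 4 | 97.28% | 96.7% | 96.60% |
| 5 | 96.76% | 96.20% | 96.10% |
| 6 | 96.26% | 95.71% | 95.61% |

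For 5 failures the Wald bound is p − 1.645·√(p(1 − p)/n) with p = 262/267 = 98.13%. At 4 failures all three pass and at 6 all three fail; 5 is the count where the method decides. The same split occurs at 277 evaluable: Wald 96.88%, Wilson 96.34%, exact 96.24%.

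**5. Error rates with 267 fixed.** Allowing up to 4 failures (the exact rule) gives type I error 4.2% and power 86.8%. Allowing up to 5 (the Wald rule) gives 9.2% and 94.7%.

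**6. Simulation.** 314 cases, 15% uniform loss unrelated to outcome, failures even or half within 90 days, 40,000 trials per scenario. Failures are kept and event-free losses dropped.
- Exact and Wald give opposite verdicts in about 11–12% of trials at a true 99% and 17–18% at a true 98%.
- Exact: power 80–82%, type I error about 2%. This is below step 5 because the downward bias adds conservatism.
- Wald: type I error roughly 5–6%.
- Kaplan-Meier, log-log interval, exact rule for zero failures: unbiased, power 85–90%, type I error 3.2–4.2%.
- Kaplan-Meier, plain Greenwood interval: type I error about 10%.

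**The case against.** The best defence is that the plan is less open than it looks. The reproduced 277 points to a binomial test, 9.3 rules out imputation, and the Kaplan-Meier curve is only a displayed summary. On the binomial reading with an exact interval the test is conservative and keeps about the planned power, and exact and Wald agree in 88–89% of simulated trials at a true 99%. All of that stands. It limits the harm but leaves the interval method unstated, and the binomial intervals themselves disagree at 5 failures.

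The second defence concerns safety. The efficacy definition adds an availability clause that the safety definition lacks. If non-censored already meant not lost, that clause would be largely redundant, so lost cases may be meant to stay in the safety set. This is a fair reading, and it is why the figure of 47 is conditional.

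A reader might infer stronger points that the documents do not support:
- *Lost cases could be counted as successes* (exact bound on 314 with 5 failures: 96.68%, a pass). That conflicts with 9.3 and with the availability clause.
- *Kaplan-Meier with a log-log interval can also go either way at 5 failures.* It gives 96.43% with even failures and 96.52% with two early ones, but those are different datasets, not two analyses of one.
- *Kaplan-Meier must be primary.* Its advantage depends on loss being unrelated to failure.
- *The plan as written leads to a false claim.* On its likeliest reading with an exact interval, the error is in the cautious direction.

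**Conclusion.** The point holds as a gap in specification with two consequences.

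First, on the ordinary meaning of the word, about 47 of 314 implanted cases would leave the safety and early-endpoint tables despite having the relevant data. This assumes the planned 15% loss and that reading of the term. The same reading understates 5-year success by about 0.1 point at a true 99% and 0.3–0.4 points at a true 96.5%, assuming loss unrelated to failure.

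Second, the primary verdict cannot be reproduced from the plan at 5 failures in 267. The unnamed interval method decides it, in roughly one trial in nine at the reference rate when exact and Wald are compared. That frequency rests on the simulation assumptions; the bounds at 5 failures need only n = 267.

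The sample size figures of 277 and 326 are not in question. The point should be fixed before the 5-year analysis.

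**What to change.** 1. **9.4.4.** Delete non-censored from both definitions. Analyse safety, 30-day fracture and seating height in all implanted cases with the relevant data.
2. **9.1.3.** Name one estimator, one denominator (stating how deaths and other-cause stem revisions enter) and one interval method. Either choice below is defensible:
   - *Evaluable-case proportion with an exact two-sided 90% interval.* This is closest to the sample size calculation, is conservative, and has power of about 80%.
   - *Kaplan-Meier 5-year estimate in all implanted cases with a log-log interval.* With zero failures, use the exact bound 0.05^(1/n), where n is the number known event-free at 5 years; it exceeds 96.5% once n is at least 85. Censor at the last date implant status is known, not the date the sponsor approves termination (10.3). State how status obtained inside the ±4-month 5-year window is used. Power is about 85–90% if loss is unrelated to failure. If lost cases fail at two or three times the rate after loss (assumed), type I error rises to 5.0–5.2% or 6.4–7.1%.
   
   Do not use a Wald or plain Greenwood interval.
3. **Sensitivity.** Report the other estimate as supportive and add an analysis for informative loss, for example with failure rates after loss multiplied by 2 and 3.

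The cost is SAP wording and a little programming, with no new data or patients. The trade-off is lower power with the proportion against reliance on uninformative loss with Kaplan-Meier.

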10.1 Subject Recruitment and Screening

Patients will be recruited at the study centers during preoperative visits through normal referral patterns. All patients recruited for this study will have the capacity to give informed consent. Advertising for the study at each center will be at the discretion of the investigator. All handouts, brochures, advertisements, etc. must be approved by the IRB/EC prior to the dissemination of any recruitment materials to potential subjects. Study advertisement content may be found in Appendix F.

10.2 Patient Informed Consent and Guidelines

All patients for this study will be provided an Informed Patient Consent Form describing this study and providing sufficient information for them to make an informed decision about their participation. The Informed Patient Consent Form must contain all elements required by the FDA under 21 CFR Part 50, in addition to any other elements required by state, local and institutional policies. For international sites, the applicable country regulations are required. See Appendix G for a copy of the Model Informed Patient Consent. This will be submitted with the protocol for review and approval by the IRB/EC for the study. All patients must provide written consent after having had adequate time to consider their participation in the study. The formal consent of a patient, using the IRB/EC approved Informed Patient Consent Form, must be obtained before that

patient is submitted to any protocol related procedures that are not part of normal care. Written documentation of consent must be provided on the Informed Patient Consent Form's signature page in addition to a note in the patient medical records indicating the date that consent was obtained. The investigator-designated research professional obtaining the consent must also sign this Informed Patient Consent Form. The patient or his/her legal representative should receive a signed copy of the Informed Patient Consent Form, according to GCP guidelines.

The procedure for obtaining informed consent is outlined below:

- Use a current IRB/EC approved copy of the Informed Patient Consent Form.
- Review thoroughly with the patient before having them sign.
- After the patient has consented to the procedures, ensure he/she signs and dates the Informed Patient Consent Form.
- The person obtaining consent also signs and dates the signature page.
- Provide a copy of the Informed Patient Consent Form to the patient.
- If required, provide the hospital with a copy of the signed Informed Patient Consent Form.
- Maintain the signed original in the patient's study chart.

10.3 Early Withdrawal of Subjects

When and How to Withdraw Subjects

In the event that the subject is discontinued by the investigative center prior to the final study evaluation, the subject will be notified by the center that he/she is no longer in the study and a Study Termination eCRF will be completed.

The following is a list of reasons for which subjects may be withdrawn and the date of termination that should be used on the Study Termination eCRF in each situation. This list is not all inclusive:

Termination Reason	Date of Termination
Death	Date of death
Investigative center termination	Date of study close-out visit
Lost to follow-up	Date Stryker termination approval given
Voluntary withdrawal	Date subject notified center of withdrawal
Revision/removal of study device	Date of revision/removal procedure
Study device not implanted	Date of surgery
Surgery not performed	Date Stryker termination approval given

At the time of study surgery it is required that the following components are implanted for each treatment group:

Secur-Fit Advanced Hip Stem with any compatible Stryker acetabular components:

- o Secur-Fit Advanced Hip Stem
- Compatible Stryker femoral head
- o Compatible Stryker acetabular insert
- Compatible Stryker acetabular liner (if used)
- o Compatible Stryker acetabular shell

Revision or removal of the Secur-Fit Advanced Hip Stem for device-related femoral fracture or aseptic loosening constitutes a failure. Revision or removal of the Secur-Fit Advanced Hip Stem for any reason requires study termination for the subject.

If revision of the femoral head or any acetabular component is required during the study, the event does not constitute a failure or study termination.

If the subject fails to return for his/her follow-up appointments, every effort should be made to contact the subject to assess his/her health status. If, after attempting to contact the subject through three documented phone calls and a certified letter, the subject still does not respond, he/she will be considered lost to follow-up. A Study Termination eCRF will be completed only after notifying Stryker of the subject's status and being given approval to terminate.

In the event a subject does not have surgery, Stryker should be contacted to discuss if/when the surgery will be rescheduled. If the surgery is rescheduled more than 4 months from the date of preoperative data collection, the subject will need to be re-consented, all preoperative data will need to be re-collected and all original preoperative data will need to be removed from the database. If the surgery is not to be rescheduled or if the subject is no longer considered an appropriate study candidate, a Study Termination eCRF may be completed **only after notifying**Stryker of the subject's status and being given approval to terminate.

When a subject completes the study according to protocol, including the final study evaluation, a Study Termination eCRF will be completed.

11 Data Management

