3.3 Number of Subjects

Cases will be enrolled until a total of 314 cases receive the Secur-Fit Advanced Hip Stem.

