8.1 Reporting of Adverse Events

The AE reporting requirements for this study are as follows:

- All AEs that meet the definition of serious and occur within the perioperative period (intraoperative to hospital discharge)
- All AEs related to the operative site, regardless of seriousness or time of occurrence

On postoperative functional evaluations, investigators and SCs will be prompted to question subjects as to whether they have seen a doctor for any reason, been hospitalized for any reason or have a current impediment to their function.

Additionally, SCs will be responsible for following up with the subjects regarding any questionable responses received on the Follow-up Questionnaire administered in postoperative years 6

through 10. If it is determined upon this further investigation that a protocol-defined AE has occurred, the SC will be responsible for completing an AE eCRF, submitting the event to Stryker and reporting to the IRB/EC, as required.

The following decision tree facilitates identification of AEs for which reporting is required under this study protocol:

[figure not shown]

Figure 4. Adverse Event Decision Tree

General Physical Examination Findings

At screening for inclusion into the study, any clinically significant abnormality should be recorded as a preexisting condition and reported on the Demographics eCRF. From the time of consent forward, any new clinically significant findings or abnormalities that meet the definition of a protocol defined AE must also be recorded and documented as an AE.

Adverse Event Reporting Period

The study period during which AEs must be reported is normally defined as the period from the initiation of any study procedures to the end of the study treatment follow-up. The start of study procedures is considered to be the point of consent. Any AEs which fit the protocol defined reportable events must be reported from the time of consent until study completion.

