9.1.2 Secondary Efficacy Parameters

The secondary efficacy parameters include:

- The all-cause revision and/or removal rates of the Secur-Fit Advanced Hip Stem;
- The rate of device-related femoral fracture among patients implanted with the Secur-Fit Advanced Hip Stem within 30 days postoperative; and
- The component exposure or countersink upon final seating intraoperative.

Additional data will be collected as noted in Section 2.1.3; related details are in Section 9.4.1 Data Summary.

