Intraoperative fissure, fracture, or perforation of the femur, acetabulum or trochanter can occur

due to impaction of the component into the prepared femoral canal or acetabulum. Postoperative

femoral or acetabular fracture can occur due to trauma, the presence of defects or poor bone

stock.

Metal sensitivity reactions have been reported following joint replacement.

AEs may necessitate reoperation, revision, arthrodesis of the involved joint, girdlestone or

amputation of the limb.

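### A case in which the stem is tried but another is left in can belong to no analysis population, so a fracture that forces the switch can miss every planned rate

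*Combined protocol and SAP*

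**What the plan says.** Two rows of the termination table in 10.3 matter here. One is "Study device not implanted", dated to surgery. The other is "Revision/removal of study device", dated to that procedure. The text after the table makes revision or removal of the stem for aseptic loosening or device-related femoral fracture a failure.

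Section 3.3 sets the counting rule: "Cases will be enrolled until a total of 314 cases receive the Secur-Fit Advanced Hip Stem". Section 9.4.4 sets the populations: "The safety population will include all non-censored subjects who received the Secur-Fit Advanced Hip Stem". The per protocol population is also made up of recipients, and "The primary and secondary efficacy analyses will be based on the per protocol population". The early fracture parameter in 9.1.2 is "The rate of device-related femoral fracture among patients implanted with the Secur-Fit Advanced Hip Stem within 30 days postoperative", and 9.1.4 keeps the same restriction.

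Reporting is wider. Section 8.1 starts the reporting period at consent. It asks for serious events from the operation to discharge, and for every operative-site event whenever it occurs. Section 11.6 lists failure to implant a specified component as a protocol deviation. Section 12.2 foresees the event: "Intraoperative fissure, fracture, or perforation of the femur, acetabulum or trochanter can occur", which it attributes to driving the component into the bone.

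The documents do not define what it means to have received or been implanted with the stem. They do not mention a stem tried and exchanged within the index operation.

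**The concern.** Membership of the analysis sets is settled by how the operation ends, and one reason for an operation to end with a different stem is the event being measured. Early device-related femoral fracture is a named secondary objective. Sections 2.2 and 12.3 also promise to compare adverse event and complication rates with published figures. If a consented patient's femur fractures and the surgeon switches stems, the event goes onto an adverse event form, but no planned population contains the patient. The fractures most likely to be lost are those serious enough to change the operation. The choice of termination code is also left open, so two centres could handle the same event in opposite ways.

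**Working it through.** **Step 1. Follow one intraoperative femoral fracture through the plan.**

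| What happened and how it is coded | Counts toward 314 (3.3) | Safety population (9.4.4) | 30-day fracture rate (9.1.2, 9.1.4) | Primary endpoint (10.3) | Recorded as an AE (8.1) |
|---|---|---|---|---|---|
| Fracture, study stem left in | Yes | Yes | Yes, if surgery falls within the window | Not a failure unless later revised | Yes |
| Different stem left in, coded as not implanted | No | No | No | Absent | Yes |
| Stem seated, then withdrawn, coded as removal | Arguably yes | Arguably yes, subject to the undefined term 'non-censored' | Same condition as row 1 | Failure, if device-related | Yes |

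Row 2 is the gap. Section 9.2.2 tabulates adverse events, but 9.4.4 bases the safety analysis on recipients, so the recorded event enters no percentage. Row 3 shows the same event becoming a primary failure under the other code.

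**Step 2. Size of the gap in the fracture rate.** The plan gives no figure to reproduce on this point, and its sample size figures do not bear on it. Let N = 314 recipients (3.3), x = fractures among recipients, k = fractures that forced a switch, and m = attempts abandoned without fracture. The values of x, k and m are assumptions.

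- Reported rate = x / 314
- Attempted-case rate = (x + k) / (314 + k + m)

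With m = 0:

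| x | Reported | k = 1 | k = 3 | k = 5 |
|---|---|---|---|---|
| 0 | 0.00% | 1/315 = 0.32% | 3/317 = 0.95% | 5/319 = 1.57% |
| 2 | 2/314 = 0.64% | 3/315 = 0.95% | 5/317 = 1.58% | 7/319 = 2.19% |
| 3 | 3/314 = 0.96% | 4/315 = 1.27% | 6/317 = 1.89% | 8/319 = 2.51% |

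The first omitted fracture moves the rate by (314 − x) / (314 × 315). That is 0.32 points at x = 0 and 311/98,910 = 0.31 points at x = 3. This difference hardly depends on x. The ratio of the two rates depends on it heavily, so the ratio is not a useful summary.

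**Step 3. Effect of attempts abandoned without fracture.** These belong in the attempted set too and pull the rate the other way, but only slightly. With x = 3, k = 1 and m = 4 the rate is 4/319 = 1.25%, against 1.27% with m = 0.

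**Step 4. What the coding choice can do to the primary test.** Assume 277 evaluable cases (the figure in 9.4.2) and an exact binomial test at one-sided 5% against 96.5%; the plan does not name the interval method. The test is passed with at most 4 failures (probability 0.033 at a true rate of 96.5%). At a true rate of 99% the expected number of failures is 277 × 0.01 = 2.8. One event coded as a removal rather than as not implanted uses one of those four.

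**The case against.** Several arguments limit this point.

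- **The event is captured.** Reporting runs from consent, 8.4 requires recording, and 11.6 logs the deviation. A reader might infer that these fractures are never counted at all. That goes too far: the gap is in the analysis sets, not in data capture.
- **Another code is available.** A reader might infer that such a case is excluded under any reading. The documents do not support this. A stem seated and then withdrawn can be read as received and removed, which 10.3 would make a failure if the fracture is device-related. That reading does not help when the femur fractures during broaching, before any stem is seated, because there is then nothing to remove.
- **A termination date is not a stop to follow-up.** A reader might infer that collection ends on the day of surgery. Section 10.3 only says which date goes on the form, and 8.1 and 8.4 waive nothing for these cases. What stands is that the two have not been reconciled.
- **Timing and attribution.** The endpoint covers device-related fracture within 30 days after surgery. If that window excludes the operation, or a broaching fracture is not device-related, a wider denominator alone would not bring the event into the fracture rate. This is correct, and the fix has to deal with it. The safety population does not depend on it.
- **The comparison.** Published rates may also count implanted stems only, and the documents do not say. The omission lowers this study's own rates; whether it distorts the comparison with the literature is unknown.
- **Consequence.** The fracture rate is descriptive, with no test or threshold.

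**Conclusion.** The point holds as a gap in the analysis populations. A case coded as not implanted fills no enrolment place and is in neither the safety population, the per protocol population nor the fracture-rate denominator. A fracture that leads to a different stem can therefore be reported and still enter no planned rate. Each such omission lowers the observed rates, by about 0.3 percentage points of the fracture rate with 314 recipients. How many there are, and so the total effect, cannot be found from the documents; the 1 to 5 cases used above are illustrative. A claim that the true rate is some multiple of the reported one would rest on those invented counts and should not be made.

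The effect on the fracture rate also assumes that intraoperative fractures count toward the 30-day endpoint and are judged device-related. The effect on the adverse event tables needs neither assumption. The primary test is touched only through the unresolved coding of a stem withdrawn during the index operation. This should be corrected, but it does not undermine the primary design.

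**What to change.** - **9.4.4:** define the safety population as all consented subjects in whom implantation of the study stem was attempted, whether or not it was left in. State the surgical step at which an attempt begins. Tabulate adverse events on this set.
- **9.1.2 and 9.1.4:** report device-related femoral fracture from surgery through 30 days, state that intraoperative fractures are included, and say whether a fracture during broaching counts as device-related. Give the rate on the attempted set beside the implanted-only rate.
- **10.3:** state how a stem exchanged during the index operation is classed, and reconcile termination dated to surgery with the reporting period in 8.1.
- Define 'received' and 'implanted', and leave the primary analysis on implanted stems.

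The cost is wording and minor extra tabulation, plus fracture and adverse event rates that may look slightly less favourable. Termination and adverse event forms should identify most of these cases; operative notes may be needed to separate a true attempt from a case in which the stem was never tried. Section 9.4.2 describes 314 as the final sample size, so enrolment may be over. The change to the analysis is still possible in that case, because the events were reportable throughout.
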